# 6 STUDY PROCEDURES

All outcomes' data will be collected from the participating HCOs' respective EHRs using existing data regularly collected to provide standard patient care and to monitor quality. Participants enrolled in the

intervention will be ‘flagged’ in the EHR as pilot participants and monitored longitudinally.

AMGA regularly collects data from HCOs on a monthly or quarterly basis for all quality improvement, research, and best practices learning collaborative programs, and has a long history of creating detailed data specifications and reporting templates to which member organizations respond and complete. Participating sites have confirmed their ability to do this for this pilot. Monthly data will be submitted to AMGA at the end of study months three, seven, and 10 (see milestones and timeline). Seven total months of EHR data will be collected from each participant: three months prior to enrollment, three months during the intervention, and one month post program discharge.

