## 1 STUDY OBJECTIVES

### 1.1 Primary Objective

The primary objective of this pilot study is to embed and test the feasibility of a novel best practice-based approach, MIND at Home, within primary care (PC) to enhance and elevate the role of existing primary care staff to Memory Care Coordinators (MCCs), increase primary care access to interdisciplinary collaborative care, and systematically combine the benefits of clinic-based services with home- or telephone/video-based assessment to support family-centered care planning and implementation for people living with dementia (PLWD) and their care partners. Our overarching goal is to test establish feasibility, acceptability, fidelity, and sample size/referral rate data for MIND at Home in PC to prepare for a future multi-site embedded pragmatic trial.

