#### **4.1 Inclusion Criteria**

Participants must meet all the inclusion criteria to participate in this study:

- Community residing adults,  $\geq 18$  years
- PLWD defined in one of two ways:
  - A diagnosis using algorithms based on CMS' Chronic Care Warehouse definition of Alzheimer's Disease, Related Dementias, Related Disorders, and Senile Dementia. This definition includes those who have an eligible ICD-9/ICD-10, CPT4, or HCPCS code on any eligible claim (i.e., inpatient, outpatient, SNF, or home health visit or stay) in the past three years or a diagnosis on the patient problem list; OR
  - A dementia medication including donepezil, donepezil/memantine combination, galantamine, rivastigmine, aducanumab, or memantine on the patient medication list or a pharmacy claim in the past three years.
- Actively receiving primary care services at one of three primary care practices within two participating health care organizations selected as study sites.
- Have a reliable care partner who speaks English (or a language spoken by the Memory Care Coordinator).
- Willing to participate in all study home or telephone/video visits and related activities for the entire length of the study (3 months).

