## 6.2 Description of Evaluations

At enrollment, basic patient information will be collected including sex, age, race, and ethnicity.

Monthly data on hospital transfers (hospitalizations, emergency department visits, observation stays without admission), number of medications, number of anti-psychotic medications, and acetylcholinesterase inhibitors and memantine medications will be collected on each enrolled patient over a 7-month period (and submitted to AMGA per schedule described above). The pre-intervention data will be collected retrospectively. Exhibit 6.1 shows the baseline (at enrollment) and monthly data collection per patient and includes 3 months of data prior to enrollment, 3 months of data during enrollment, and 1 month of data post-enrollment. All data will be collected from site EHRs using data collected as part of routine clinical care.

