#### Screening by Clinic Staff

PLWD will be identified in the EHR of their respective HCOs, by clinic staff, as ever having a diagnosis of ADRD or prescription for a dementia-related medication, on an administrative claim, patient problem list (Dx), or patient medication list (Rx) for the duration of time the patient has data in the EHR. Patients with an existing diagnosis of mild cognitive impairment may be assessed for ADRD during the visit by their provider. Patients must be living at home and in the care of an informal care partner. Patients eligible for the study based on EHR data will be flagged prior to their visit. Once the provider has confirmed eligibility by confirming diagnosis or medication and living situation, eligible PLWDs and their care partners will be invited to participate in the program. For PLWD without a scheduled visit, care partners/PLWD will be contacted by telephone to enroll in the program using a script, based on local context and cultural adaptation of an existing script. (See Appendix D.)

After establishing eligibility, enrollment will be initiated by scheduling an initial home, telephone, or video visit with the MCC. Enrollment will begin with a needs assessment (JHDCNA) during the intake visit.

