## 8 **INTERVENTION DISCONTINUATION**

The intervention may be voluntarily discontinued by a subject at any time. In addition, if a subject is permanently transferred from their home to a long-term care facility, they will no longer be eligible to continue the study. There are no other reasons to discontinue a subject from the intervention as long as they continue to live at home, have an informal care partner, and are willing to participate.

We will continue to collect data on subjects who withdraw voluntarily from participation in the study. All data collection is passive, pulled from the EHR where the subject receives their regular primary care.

Subjects who discontinue before the study has completed will be replaced, if possible, as long as this does not extend the length of the study.

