## 9.2 Sample Size and Randomization

The pilot study is not powered to detect significant changes in our selected outcome measures. However, we estimated power, nonetheless. Preliminary studies of the MIND at Home program report a reduction from 1 to 0.73 in number of hospital admissions per year, or a 27% decrease. Our primary outcome is hospital transfers (which includes admissions but also ER visits and observation stays without admissions), but we expect that the relative effect size on this outcome will be similar to hospital admissions alone. Because our observation periods are 3 months (as opposed to 1 year), our assumed base rate is 0.50. To make our power estimates slightly conservative, we will assume an effect size of 25%. Given these factors, the estimated power is 37.5% to detect the effect (Z-test with square root adjustment for low base rates). This low power is primarily caused by the short duration of the intervention per patient in the pilot, making outcome observations (transfers) very rare. In the full trial we will use a 12-month intervention period.

For the full trial, sample size estimates will be based on the primary outcome (hospital transfer rate over 12 months). We intend to implement a cluster-controlled cohort design with a baseline period, which requires specialized power calculations (Hemming et al., 2020). Calculations will assume a Poisson distribution of hospitalization rates, equal cluster sizes, and an equal number of clusters in the treatment and control arms. Because validated estimates of correlations are not available, we will use conservative assumptions for intra-cluster correlation (0.05) and individual autocorrelation (0.2). Baseline hospital transfers are estimated to occur at a rate of 1 transfer per year. Assuming this rate, the study will be powered to detect a 0.2 absolute reduction (20% relative reduction) at greater than an 80% power level. This will require at least 11 clusters in each arm of two study arms, with each practice recruiting approximately 50 patients. Analysis of the full study will make use of mixed-model ANCOVA, controlling for both patient level and cluster level confounding variables.

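### The pilot extracts only three pre-enrollment months of transfers for a full trial sized on a 12-month rate; a 12-month look-back from the same EHR pull would be a cheap improvement

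*Combined protocol and SAP*

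**What the plan says.** **Window.** Section 6 sets the extract: "Seven total months of EHR data will be collected from each participant: three months prior to enrollment", then three months on the program and one after discharge. The table in 6.1 and sections 6.2, 9.4, 9.5 and 10.1 repeat it.

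**How the data are obtained.** Section 6.2 says: "The pre-intervention data will be collected retrospectively". Section 8 adds: "All data collection is passive, pulled from the EHR where the subject receives their regular primary care".

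**History already searched.** The inclusion criteria in 4.1 look for a qualifying code "on any eligible claim (i.e., inpatient, outpatient, SNF, or home health visit or stay) in the past three years". Screening in 6.2.1 looks for a diagnosis or dementia drug "for the duration of time the patient has data in the EHR".

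**What the pilot is for.** Section 1.1 includes in the overarching goal "sample size/referral rate data for MIND at Home in PC to prepare for a future multi-site embedded pragmatic trial".

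**What the full trial needs.** Section 9.2: "For the full trial, sample size estimates will be based on the primary outcome (hospital transfer rate over 12 months". It assumes 1 transfer per year, Poisson counts, an intra-cluster correlation (ICC) of 0.05 and an individual autocorrelation of 0.2. On the correlations it says: "Because validated estimates of correlations are not available, we will use conservative assumptions".

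**Stated use of the window.** Section 9.5 compares the pre-enrollment rate with the rate in the three enrolled months. Section 9.5 also plans exploratory work on the reliability and missingness of covariates, including baseline outcome rates. It names no 12-month rate or dispersion estimate.

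**The concern.** The full trial's outcome is a 12-month count, while the pilot's only untreated outcome data are three monthly counts per enrollee. An annual rate then has to be scaled up from one quarter, and the spread of 12-month counts can be reached only through a model. The data come from a retrospective query at sites that already search years of records, so a longer window needs no participant contact.

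The full trial's size depends on both quantities. The number of clusters varies inversely with the base rate, and any overdispersion beyond Poisson raises it further. The base rate is also unsettled within section 9.2: 0.50 per three-month period for the pilot, which is 2 per year, against 1 per year for the full trial.

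**Working it through.** **Inputs from the documents:** 150 enrollees; look-back T = 0.25 year; pilot base rate 0.50 per period with a 25% reduction; full-trial base rate 1 per year with a 20% reduction; 50 patients per cluster; ICC 0.05; individual autocorrelation 0.2; three practices.

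**Assumed here:** two-sided 5% test, cluster autocorrelation 1, frailty variance v of 0 to 2. The documents give none of these.

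**1. Pilot power (stated 37.5%).** Square-root Poisson Z-test, periods treated as independent:
Φ[2(√0.50 − √0.375)/√(2/150) − 1.96] = Φ(1.641 − 1.96) = 37.5%. This reproduces the figure and confirms that 0.50 is a three-month count, so 0.50 × 4 = 2 per year. At 1 per year (0.25 per period) the same formula gives 21.2%.

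**2. Full-trial size (stated at least 11 clusters per arm).**
- Design effect: 1 + 49 × 0.05 = 3.45.
- Baseline correlation: r = (50 × 0.05 + 0.95 × 0.2)/3.45 = 0.780, so 1 − r² = 0.392.
- SE with 11 clusters: √[(1 + 1)/(11 × 50) × 3.45 × 0.392] = 0.070.
- Power: Φ(0.2/0.0701 − 1.96) = 81.4%. Ten clusters give 77.6%.

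So 11 reproduces under these settings. It is sensitive to the unstated cluster autocorrelation: at 0.9, 11 clusters give 71.4%.

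**3. Precision of the annual rate.** Var = (λ/T + vλ²)/150; relative half-width = 1.96 × SE/λ.

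| λ per year | v | 3 months (37.5 person-years) | 12 months (150 person-years) |
|---|---|---|---|
| 1 | 0 | SE 0.163, 32% | SE 0.082, 16% |
| 1 | 1 | SE 0.183, 36% | SE 0.115, 23% |
| 2 | 0 | SE 0.231, 23% | SE 0.115, 11% |
| 2 | 1 | SE 0.283, 28% | SE 0.200, 20% |

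These treat patients as independent.

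**4. Allowing for three practices.** Apply ICC 0.05 to the 12-month variance at λ = 1. For Poisson counts the between-practice variance is 0.05, which adds 0.05/3 = 0.0167.
- 3 months: √(4/150 + 0.0167) = 0.208, half-width 41%.
- 12 months: √(1/150 + 0.0167) = 0.153, half-width 30%.

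With v = 1 the between-practice variance is 0.10, and the same steps give 51% and 42%. The between-practice part does not shrink with a longer window.

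**5. What this means for the full trial's size.** With the settings of step 2, clusters needed for 80% power go as 1/λ. Across the independent-patient Poisson intervals at λ = 1:
- 3 months, 0.68 to 1.32: 16 down to 9 clusters per arm.
- 12 months, 0.84 to 1.16: 13 down to 10.

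At a true rate of 0.68, 11 clusters give 65% power.

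**6. Dispersion.** At λ = 1, v = 0.5, 1 or 2 raises the need from 11 to 16, 22 or 32 clusters. The variance-to-mean ratio of a count over T years is 1 + vλT. With λ = 1 and v = 1 it is 1.25 over three months and 2 over twelve, so departure from Poisson is much easier to see in 12-month counts.

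**The case against.** **The window has a purpose.** A reader might infer that three months was chosen for no reason. That is not so: sections 9.2 and 9.5 set equal three-month pre and during periods for a direct comparison, and that choice is coherent. Aim 3 concerns the feasibility of ascertaining outcomes, and sections 9.1 and 9.5 call the work unpowered and exploratory. Sample-size data could also be read as recruitment yield. This stands as a reason to keep the three-month comparison and to treat the point as an improvement. It does not explain why the extract must stop there.

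**Correlations.** A reader might infer that a longer look-back supplies the estimates that 9.2 says are missing. It does not. Those are the ICC and the individual autocorrelation. Three practices cannot give a useful ICC with any window, and correlation between two 12-month periods needs about 24 months. Seven monthly counts already allow model-based, imprecise estimates of dispersion and of pre/during correlation.

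**Season.** A reader might infer that the base rate reflects a single season, or that season could imitate a treatment effect. If enrollment takes 16 to 22 weeks (three or two coordinators assumed), pre windows span 29 to 35 calendar weeks. With uniform enrollment, at most 69% or 58% of pre-enrollment person-time falls in any 13-week period. A during/pre ratio of 0.80 to 0.91 with no effect requires an assumed seasonal swing of 10% to 20% at the worst phase. The documents support neither assumption.

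**Precision gain.** Once practices are allowed for, the gain is smaller (41% to 30%), and even 12 months does not reach the 20% effect of interest in that case. This stands.

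**Data quality.** Active patients are those with any service in three years (3.2), so finding a qualifying code does not show complete capture of transfers. Some enrollees may be newly diagnosed after mild cognitive impairment (6.2.1), so early months may precede diagnosis. Both are limits to report.

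**Conclusion.** The point holds as a cheap design improvement. It shows no error in a stated figure: 37.5% and 11 clusters both reproduce, and a three-month rate can be annualised, only less precisely.

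At 1 transfer per year, moving from 3 to 12 months cuts the half-width from about 32% to 16% for independent Poisson patients. With frailty variance 1 the cut is from 36% to 23%, and with ICC 0.05 over three practices it is from about 41% to 30% (Poisson). The first of these is the most favourable case. The more durable gain is that 12-month counts let the Poisson assumption of 9.2 be checked directly; that assumption moves the cluster number more than the base rate does across the ranges shown. The disagreement between 2 and 1 per year within 9.2 makes a better base rate more useful.

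The results rest on the assumed frailty variance, on normal approximations and, for cluster numbers, on cluster autocorrelation 1. The look-back rate describes people alive and community-residing at enrollment. It is not the rate over 12 months of follow-up.

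**What to change.** In section 6, the table in 6.1, and sections 6.2, 9.4, 9.5 and 10.1:

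- Extend the retrospective transfer extract to months -12 to -1 for the 150 enrollees. Keep months -3 to -1 as the baseline for the pre/during comparison.
- Report the annual transfer rate per observed person-time, the variance-to-mean ratio of 12-month counts and, descriptively, the quarter-to-quarter within-patient correlation.
- State that these do not give the ICC or the correlation between two 12-month periods, and that the rate applies to patients alive and community-residing at enrollment.
- Optionally, as a check on season, compare the during window with the same calendar months one year earlier.
- Reconcile the two base rates in 9.2.
- Extend the validation arm only if an index date is defined for it. Those 100 patients have no enrollment date, and 11.2 describes them as not currently seeking care.

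**Cost.** Nine more monthly rows per patient (9 × 150 = 1,350) in an existing query, a protocol amendment, and an IRB and HIPAA-waiver modification to cover the longer window. Section 11.2 puts IRB review of a consent-protocol change at 3 to 4 weeks. The chart review in 10.1 may grow. Older months will be incomplete for patients new to the organization or with outside care; flag them and count only observed person-time.

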## 6.1 Summary of primary and secondary outcome measures by data collection interval relative to patient enrollment

Outcome Measure	Study Month -3	Study Month -2	Study Month -1	Baseline/ Enrollment Study Month 0	Study Month 1	Study Month 2	Study Month 3	Post Study Month 4
Hospital Transfers (hospitalizations, ED visits, observation stays)	X	X	X		X	X	X	X
Number of Medications	X	X	X		X	X	X	X
Number of Anti-psychotics Rx	X	X	X		X	X	X	X
Number of acetylcholinesterase inhibitors Rx	X	X	X		X	X	X	X
Number of memantine Rx	X	X	X		X	X	X	X
Sex				X				
Age				X				
Race				X				
Ethnicity				X				
Rural Residence				X				
Comorbidities				X				

## 6.2 Description of Evaluations

At enrollment, basic patient information will be collected including sex, age, race, and ethnicity.

Monthly data on hospital transfers (hospitalizations, emergency department visits, observation stays without admission), number of medications, number of anti-psychotic medications, and acetylcholinesterase inhibitors and memantine medications will be collected on each enrolled patient over a 7-month period (and submitted to AMGA per schedule described above). The pre-intervention data will be collected retrospectively. Exhibit 6.1 shows the baseline (at enrollment) and monthly data collection per patient and includes 3 months of data prior to enrollment, 3 months of data during enrollment, and 1 month of data post-enrollment. All data will be collected from site EHRs using data collected as part of routine clinical care.

### 6.2.1 Screening Evaluation

We have requested a waiver of informed consent.

#### Screening by Clinic Staff

PLWD will be identified in the EHR of their respective HCOs, by clinic staff, as ever having a diagnosis of ADRD or prescription for a dementia-related medication, on an administrative claim, patient problem list (Dx), or patient medication list (Rx) for the duration of time the patient has data in the EHR. Patients with an existing diagnosis of mild cognitive impairment may be assessed for ADRD during the visit by their provider. Patients must be living at home and in the care of an informal care partner. Patients eligible for the study based on EHR data will be flagged prior to their visit. Once the provider has confirmed eligibility by confirming diagnosis or medication and living situation, eligible PLWDs and their care partners will be invited to participate in the program. For PLWD without a scheduled visit, care partners/PLWD will be contacted by telephone to enroll in the program using a script, based on local context and cultural adaptation of an existing script. (See Appendix D.)

After establishing eligibility, enrollment will be initiated by scheduling an initial home, telephone, or video visit with the MCC. Enrollment will begin with a needs assessment (JHDCNA) during the intake visit.

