#### **3.2 Study population and eligibility**

*Community residing* adults,  $\geq 18$  years, living with dementia and who are actively receiving primary care services at one of the three study primary care practices within two participating health care organizations (HCOs) will be targeted. Active patients are defined by the HCO but typically include patients who have received any type of health care service from the HCO in the past three years. PLWD will be defined using algorithms based on CMS' Chronic Care Warehouse definition of Alzheimer's Disease, Related Dementias, Related Disorders, and Senile Dementia. This definition includes those who have an eligible ICD-9/ICD-10, CPT4, or HCPCS code on any eligible claim (i.e., inpatient, outpatient, SNF, or home health visit or stay) in the past three years, a diagnosis on a patient problem list, or a prescription for a dementia-related medication (see Section 4.1 for list). Eligible PLWD must also have a reliable care partner who speaks English (or a language spoken by the MCC) and who is willing to participate in all study home, telephone, or video visits and related activities. PLWD in crises (e.g., show signs of abuse, neglect, extreme risk of danger to self or others), will be referred to receive appropriate services, but will be excluded from the study.

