#### **4.3 Study Enrollment Procedures**

PLWD will be identified in the EHR of their respective HCOs and approached in two ways. PLWD who present with their care partners for an outpatient office visit will be invited to participate in the program and provided a program information sheet (see Appendix C). After establishing eligibility, dyads can choose to enroll by scheduling an initial home or telephone/video visit with the MCC. Enrollment will begin with an initial needs assessment (the JHDCNA, Appendix B) during a home or telephone/video visit. Telephone intake will be supplemented with a home visit at a later date or photos of the living situation to identify safety issues or ways to improve the PLWD's care. Sites will also identify PLWD in the EHR who meet program eligibility criteria but are not scheduled for a visit. To ensure equity, racial minorities and other underserved populations will be prioritized and approached using culturally sensitive processes to ensure a representative sample of participants. Care partners/PLWD will be contacted by telephone to enroll in the program using a script, based on local context and cultural adaptation of an existing script (see Appendix D). Recruitment will be supported with existing MIND outreach and engagement resources. To assess feasibility and validity of eligible patient identification, referral, and enrollment, MCCs will electronically record the number of patients flagged as eligible, referred, enrolled, and retained or who refused, were unreachable, or lost to follow-up. Referral, recruitment, patient acceptance, and attrition rates will be calculated to assess the feasibility of use of the algorithm and of the

recruitment protocol. MCCs will enroll a minimum of seven PLWD every other week for a maximum caseload of 42, to accommodate other non-dementia patients who may be part of the MCC total caseload.

As this is a minimal risk, best-practice based quality improvement intervention, a waiver of consent will be requested for this study for both the intervention patients and the data validation arm cohort. Further justification is described in section 11.2.

Patients will not be randomized for this pilot study.

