## 10.2 Data Management

Clinic study sites are responsible for data collection and management as described above. MCCs will collect data on study feasibility, validity of patient identification, and intervention fidelity. Information technology staff at participating organizations will be responsible for extracting data on participants from their EHRs and working closely with the AMGA research analyst during the file transfer process to ensure confidentiality and protection of participant data.

AMGA staff will be responsible for working closely with clinic site investigators and clinic staff in the collection of study data. Once data are transferred through a secure Dropbox link, AMGA staff will be responsible for maintaining and protecting the confidentiality of all study data. AMGA staff will keep the

password-protected files on secure servers on password-protected computers. Only the AMGA research analyst, biostatistician, and study PI will have access to study data.

Study feasibility, validity, and fidelity data will be collected using Excel spreadsheets that are password protected. EHR data will be abstracted by the study sites using their usual methods of extracting data for quality purposes. Data will be sent to AMGA as csv files.

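### The Aim 1 counts have no category for flagged patients found ineligible and leave referral undefined, so a poor flag cannot be told from limited outreach; the screening look-back wording also needs reconciling

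*Combined protocol and SAP*

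**What the plan says.** **Counts.** Aim 1 (Précis, Design and Outcomes) covers both the feasibility and the validity of identifying eligible patients. Section 10.2 states: "MCCs will collect data on study feasibility, validity of patient identification, and intervention fidelity". Section 4.3 lists what is logged: "MCCs will electronically record the number of patients flagged as eligible, referred, enrolled, and retained or who refused, were unreachable, or lost to follow-up". Section 10.1 repeats the list and says that referral, recruitment, acceptance and attrition rates will be used to judge the algorithm and the recruitment protocol. No numerator or denominator is given there or in section 9.5.

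**Flag and confirmation.** Section 6.2.1 states: "Patients eligible for the study based on EHR data will be flagged prior to their visit". The invitation follows a provider check: "Once the provider has confirmed eligibility by confirming diagnosis or medication and living situation". Patients without a scheduled visit are telephoned, and the text does not say how their eligibility is established.

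**Look-back.** Section 6.2.1 identifies patients "as ever having a diagnosis of ADRD or prescription for a dementia-related medication, on an administrative claim", or on the problem or medication list, over all the time they have EHR data. Section 4.1 requires a dementia code "on any eligible claim (i.e., inpatient, outpatient, SNF, or home health visit or stay) in the past three years" or a problem-list diagnosis, or else a dementia medication "on the patient medication list or a pharmacy claim in the past three years". Section 3.2 gives the claim window in similar terms: "in the past three years, a diagnosis on a patient problem list, or a prescription for a dementia-related medication".

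**The concern.** A pilot that sets out to test an EHR algorithm should be able to say, of the patients it flagged and someone then assessed, how many were eligible. A flagged patient whose diagnosis is not confirmed, who does not live at home, who has no suitable care partner or who is in crisis fits none of the listed counts. Nor does a flagged patient whom nobody approached. The two groups merge in whatever is left over.

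They call for different changes before the full trial: a better algorithm in one case, more outreach capacity in the other. Referral-rate data are a stated goal of the pilot, and reasons for ineligibility that are not logged at the time may be hard to recover later.

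The look-back difference adds a smaller risk. With two windows in the text, sites could build different flags, and their flagged denominators would not be comparable.

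**Working it through.** **1. Does another part of the plan supply the missing count?**
- The chart review in section 10.1 is in the Aim 3 paragraph on patient-level outcomes.
- The data validation arm (section 11.2.1.3) is for extraction feasibility and data quality.
- The safety report (section 7.7) includes a number screened, which is not defined and has no ineligible counterpart.
- The intake screen (section 3.1) is described as establishing interest and identifying the care partner.
- Section 9.5 defines no Aim 1 measure.

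None of these is stated to record whether a flagged patient was eligible.

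**2. What could referral mean?**
- Passed on after provider confirmation: enrolled/referred then approximates uptake among confirmed patients, but flagged minus referred still mixes ineligible patients with those not approached.
- Entry by primary care referral (section 3.1) or from other providers (section 4): the count then describes entry route and says nothing about ineligible flags.

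**3. What the listed counts can show (illustration).** The plan states no figure to reproduce. Enrolled E = 150 is the target. All other inputs are assumptions: refused R = 60, unreachable U = 30, and r = 30, 60 or 120 flags with no recorded outcome. All enrolled and refused patients are taken as flagged and eligible. Flagged F = E + R + U + r.

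| | r = 30 | r = 60 | r = 120 |
|---|---|---|---|
| F | 270 | 300 | 360 |
| Eligible share, lower: (E+R)/F = 210/F | 77.8% | 70.0% | 58.3% |
| Upper, if the remainder may be unapproached | 100% | 100% | 100% |
| Upper, if every flag was worked to one outcome: (E+R+U)/F = 240/F | 88.9% | 80.0% | 66.7% |
| Enrolled per eligible flag, lower: 150/F | 55.6% | 50.0% | 41.7% |
| Enrolled per eligible flag, upper: 150/210 | 71.4% | 71.4% | 71.4% |

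Two assumptions flatter the lower bound. At F = 300, if refusers' eligibility is unknown, it falls to 150/300 = 50%. If instead 30 of the 150 enrolled (assumed) came by another route, it is (120 + 60)/300 = 60%.

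The referred count is not used here. On the first reading in step 2 it would give a firmer lower bound, referred/F, but it would not move the 100% upper bound.

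**4. What an ineligible count adds.** Take F = 300 and x = 20, 40 or 60 assessed and found ineligible (assumed).
- Confirmed/assessed, all refusers confirmed first: 210/(210+x) = 91.3%, 84.0%, 77.8%.
- Confirmed/assessed, no refuser assessed: 150/(150+x) = 88.2%, 78.9%, 71.4%.
- Not approached: 300 − 150 − 60 − 30 − x = 40, 20, 0, valid only if outcomes are mutually exclusive.
- Share over all 300 flags, refusers eligible: 210/300 to (300−x)/300, that is 70–93.3%, 70–86.7%, 70–80%.

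The share among assessed flags becomes an estimate. The share over all flags is still a range. These are different quantities, and the first does not narrow the second. The gap between the first two lines shows why confirmed eligible must be counted directly.

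**5. Look-back, source by source.**

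| Evidence | 6.2.1 | 3.2 | 4.1 | Conflict |
|---|---|---|---|---|
| Diagnosis code on a claim | any time | three years | three years | yes |
| Pharmacy claim | any time | no window; points to 4.1 | three years | with 4.1 |
| Problem list | any time | no window | no window | no |
| Medication list | any time | no separate window | unclear whether the limit applies | unclear |

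The conflict is therefore confined to patients whose only evidence is an older claim. They can be identified under 6.2.1 and still fail 4.1.

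**The case against.** **The look-back is a broad pull narrowed by a flag.** Section 6.2.1 identifies first and then flags those eligible on EHR data, section 10.1 deploys the algorithm based on the CMS definition to find eligible patients, and section 4.1 requires every inclusion criterion to be met. This is a fair reading and much of it stands, which is why the point is minor. It does not close the gap: the only look-back that 6.2.1 states is unlimited, and its provider check names no window.

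**Referral is one step in a sequence.** The listed order, and the order in Aim 1, suggest flagged, then referred, then enrolled. That is the more natural reading, and it yields a usable uptake ratio. It leaves the mixture in flagged minus referred.

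**The log itself is not shown.** Section 10.2 promises data on validity, and the spreadsheet may hold more fields than the summary sentence lists. That is possible, and absence from a summary is weaker evidence than absence from the form. But the plan names no validity measure, and the same seven counts appear in both sections that list them.

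**The pilot is exploratory.** Section 9.1 states no hypothesis, and no outcome analysis, sample size or safety rule depends on these counts. That limits the consequence to Aim 1.

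A reader might infer more: that the flag is inaccurate, that ineligible patients will be enrolled, or that Aim 1 cannot be answered at all. The documents support none of these. They do not size the older-claim group, the provider check may catch some misflagged patients, and acceptance among invited patients can be calculated from the counts as listed.

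**Conclusion.** The concern holds for the counts. A log kept exactly as sections 4.3 and 10.1 list it cannot separate flagged patients who were ineligible from flagged patients who were not approached, although validity of identification is a named aim. The definition of referral matters, but no reading of it removes the problem. The look-back difference is real and narrow, and needs only a reconciliation of wording.

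The size is unknown, because the documents give no flagged count or dispositions. The ranges above show only how the counts behave. They rest on assumed refusals, unreachable patients and unresolved flags, on every enrolled patient having come through the flag, and on refusers having been eligible. The conclusion that the share is bounded but not estimated does not depend on those values, provided some flags end without a recorded outcome. A reader might also infer that adding an ineligible count would settle the share over all flags. It would not, as long as some flagged patients are never assessed.

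**What to change.** - Reconcile the look-back wording in sections 3.2, 4.1 and 6.2.1, including whether the window in 4.1 covers the medication list, so that the flag implements the eligibility rule. Which window to use is for the investigators.
- In the MCC log, give each flagged patient one mutually exclusive screening status: assessed and confirmed eligible; assessed and found ineligible, with reason; refused before assessment; unreachable; not approached. Among those confirmed eligible, record enrolled or refused.
- Record entry route (EHR flag, primary care or outside referral, new diagnosis at a visit), define referral, and state the denominator of each Aim 1 rate.
- Report confirmed eligible/assessed among EHR-flagged patients descriptively by site, and name it as the validity data promised in section 10.2. Describe it as provider or chart confirmation, not as a predictive value against a gold standard, and note that the share over all flags remains a range.

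The cost is some protocol wording and a few extra entries in a log that is already planned. Providers must pass the reason for non-confirmation to the MCC. No additional patient contact is needed.
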